#### 5 ENDPOINTS

## 5.1 Primary Endpoints

The primary objectives relate to safety, tolerability, and determining the RP2D of BMS-986277 alone and/or in combination with nivolumab in advanced epithelial tumors. These will be measured by the following endpoints.

#### 5.1.1 Adverse Events

- Incidence rate of adverse events (AEs), serious adverse events (SAEs), AEs meeting the protocol-defined DLT criteria (Protocol Section 7.4.1), AEs leading to discontinuation, and AEs resulting in death
  - DLTs are identified as recorded on the case report form (CRF).
  - All non-serious AEs will be assessed from the start of dosing.
  - All SAEs and deaths will be assessed from the date of the participant's written informed consent.
  - All AEs (serious and non-serious), and deaths will be assessed up to 30 days after the last dose of BMS-986277 for participants enrolled in Part 1 or 100 days after the last dose of any study drug for participants enrolled in Parts 2 and 3.
  - Drug-related AEs are those events with relationship to study drug "Related", as recorded on the CRF. If the relationship to study drug is missing, the AE will be considered as drugrelated.
  - Serious adverse events consist of AEs deemed serious by the Investigator and flagged accordingly in the CRF and clinical database.
  - Adverse events leading to study drug discontinuation are AEs with action taken = "Drug was discontinued".
  - AEs belonging to select AE categories will be assessed using the categorizations which are current at the time of database lock. An accompanying listing will be provided to define the categorizations at each analysis.

- ♦ The select AE categories from the CA209 dictionary will be used, as well as any additional categories and/or AEs within a category that may be particularly relevant or of interest for BMS-986277.
- Immune-mediated AEs may also be summarized if warranted based on sufficient data, relevance, interest, etc.
- AEs will be coded using the most current version of the Medical Dictionary for Regulatory Activities (MedDRA) at the time of each database lock
- AEs will be graded for severity according to the National Cancer Institute (NCI) Common Terminology Criteria for Adverse Events (CTCAE) version 4.03.

# 5.1.2 Clinical Laboratory Test Abnormalities

- Incidence of clinical laboratory test abnormalities
  - Any laboratory test result that is clinically significant or meets the definition of an SAE
  - Any laboratory test result abnormality that required the participant to have study treatment discontinued or interrupted
  - Any laboratory test result abnormality that required the participant to receive specific corrective therapy
  - Laboratory values will be graded according to the NCI CTCAE version 4.03.
  - Potential drug induced liver injury (DILI) events are defined as:
    - ◆ AT (ALT or AST) elevation > 3 times upper limit of normal (ULN) AND
    - ◆ Total bilirubin > 2 times ULN, without initial findings of cholestasis (elevated serum alkaline phosphatase),

**AND** 

♦ No other immediately apparent possible causes of AT elevation and hyperbilirubinemia, including, but not limited to, viral hepatitis, pre-existing chronic or acute liver disease, or the administration of other drug(s) known to be hepatotoxic.

# 5.1.3 Vital Sign Abnormalities and Other Safety Biomarkers

- Vital signs collected as a continuous variable (eg, blood pressure) or categorical variable (eg, Eastern Cooperative Oncology Group [ECOG] performance status)
- Measures of renal function
  - MedDRA Preferred Terms: Nephritis and Renal Failure
  - Laboratory values for Blood Creatinine
- Measures of bladder hemorrhage
  - MedDRA Preferred Term: Urinary Bladder Hemorrhage
- Measures of cytokine release monitoring
  - MedDRA Preferred Term: Cytokine Release Syndrome

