**DOCUMENT HISTORY**

Document	Date of Issue	Summary of Change
Revised Protocol 06	15-Aug-2018	Incorporates Administrative Letter 03 and clarifies that treatment algorithm in Appendix 10 applies to both infusion reactions and cytokine release syndrome. The revisions also includes title change to Appendix 5 to clarify that the algorithms are applicable to both nivolumab and BMS-986277-mediated IMAE.
Administrative Letter 03	04-Jun-2018	To add the IND number on the title page of the protocol.
Revised Protocol 05	18-May-2018	
To add an additional expansion cohort and long-term follow-up requirements as well as limit BMS-986277 dosing to 2 cycles:
 
 
• Schedule of Activities tables were updated
 
• Clinical experience with enadenotucirev was updated
 
• [REDACTED]
 
• Overall design was updated
 
• Blinded independent central review of efficacy scans was clarified
 
• [REDACTED]
 
• [REDACTED]
 
• [REDACTED]
 
• Inclusion and exclusion criteria were updated
 
• Lifestyle restrictions were added
 
• Treatments administered were updated
 
• Dose-limiting toxicities were updated
 
• Treatment delays were updated
 
• Prohibited and/or restricted treatments were updated
 
• Efficacy assessments were updated
 
• Imaging assessments were updated
 
• Adverse event and serious adverse event information was updated
 
• Pregnancy was updated
 
• Clinical safety laboratory assessments were updated
 
• Pharmacokinetic section and tables were updated
 
• Additional research collection was updated
 
• [REDACTED]
 
• Statistical considerations was updated
 
• Appendices 1, 2, 3, 4, and 8 were updated
 
• Appendix 11 was added
 
 
Typographical errors were corrected, and edits were made for consistency and clarity.

Revised Protocol 04	02-Mar-2018	To implement revisions requested by a health authority [REDACTED]

Document	Date of Issue	Summary of Change

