#### 4 OBJECTIVES AND ENDPOINTS

**Table 4-1: Objectives and Endpoints**

Objectives	Endpoints
Primary	

 
To characterize the safety and tolerability of BMS-986277 administered alone and in combination with PD-1 inhibitor, nivolumab, in advanced epithelial tumors
 
To determine the RD and RP2D and dosing schedule of BMS-986277 administered alone and in combination with nivolumab in participants with advanced epithelial tumors
 
	
 
Incidence of AEs, SAEs, AEs meeting protocol-defined DLT criteria, AEs leading to discontinuation, and AEs resulting in death
 
Incidence of clinical laboratory test abnormalities
 
Vital sign abnormalities or other safety biomarkers
 

Secondary	

 
To explore the preliminary anti-tumor activity of BMS-986277 alone and in combination with nivolumab in participants with advanced epithelial tumors (RECIST v1.1 and PCWG3)
 
To assess the PK and IMG of BMS-986277 in blood following monotherapy or combination treatment
 
	
 
ORR, DCR, mDOR, mPFS, and PFSR at 8, 16, and 24 weeks depending on indication
 
Summary measures of PK and IMG parameters of BMS-986277
 

Abbreviations: AE = adverse events; BICR = blinded independent central review; DCR = disease control rate; DLT = dose-limiting toxicity; IMG = immunogenicity; iRECIST = immune Response Evaluation Criteria in Solid Tumors; mDOR = median duration of response; mOS = median overall survival; mPFS = median progression-free survival; NPV = negative predictive value; ORR = objective response rate; OS = overall survival; OSR = overall survival rate; PCWG3 = Prostate Cancer Clinical Trials Working Group 3; PK = pharmacokinetics; PFSR = progression-free survival rate; PPV = positive predictive value; RD = recommended dose; RECIST = Response Evaluation Criteria in Solid Tumors; RP2D = recommended Phase 2 dose; SAE = serious adverse events; TPR = true positive rate

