**Table 9.4.5-1: Clinical Laboratory Tests**

Other Analyses
Serum or urine pregnancy test (WOCBP only, minimum sensitivity 25 IU/L or equivalent units of HCG).
Follicle stimulating hormone (FSH) screening -only required to confirm menopause in women < age 55).
Urinalysis including protein, glucose, blood, leukocyte esterase, specific gravity, PH.
Urinalysis or urine dipstick. If blood, protein or leukocytes esterase are positive on the dipstick, microscopic examination of the sediment is required.

A local laboratory will perform the analyses and will provide reference ranges for these tests.

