### 10.3.2 Safety Analyses

All safety analyses will be performed on the treated population.

Endpoint	Statistical Analysis Methods
Incidence of AEs, SAEs, AEs meeting protocol-defined DLT criteria, AEs leading to discontinuation, AEs resulting in death, and deaths AEs will be graded according to CTCAE v4.03	DLT rate by dose level; frequency distribution of treated participants with AE using the worst CTC grade. Participants will only be counted (1) once at the PT level, (2) once at the SOC level, and (3) once in the “total participant” row at their worst CTC grade, regardless of SOC or PT.
Incidence of clinical laboratory test abnormalities Laboratory values will be graded according to CTCAE v4.03	Laboratory shift table using the worst CTC grade on treatment per participant
Vital sign abnormalities or other safety biomarkers	Summary tables of vital signs Frequency statistics of renal function and bladder hemorrhage

Abbreviations: AE = adverse event; CTC = common terminology criteria; CTCAE = common terminology criteria for adverse events; DLT = dose-limiting toxicity; PT = preferred term; SAE = serious adverse event; SOC = system organ class

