### 8.6.9 Immune-Mediated Adverse Events

In order to further characterize AEs of special clinical interest, analysis of immune-mediated AEs (IMAEs) will be conducted. Immune-mediated AEs are specific events (or groups of PTs describing specific events) that include pneumonitis, diarrhea/colitis, hepatitis, nephritis/renal dysfunction, rash, endocrine (adrenal insufficiency, hypothyroidism/thyroiditis, hyperthyroidism, diabetes mellitus, and hypophysitis), and other specific events, considered as potential immune-mediated events by investigator, that meet the definition summarized below:

- those occurring within 30 or 100 days of the last dose for Part 1 or Parts 2-3, respectively,
- regardless of causality,

- treated with immune-modulating medication (of note, endocrine adverse events such as adrenal insufficiency, hypothyroidism/thyroiditis, hyperthyroidism, diabetes mellitus, and hypophysitis are considered IMAEs regardless of immune-modulating medication use, since endocrine drug reactions are often managed without immune-modulating medication).
- with no clear alternate etiology based on investigator assessment, or with an immune-mediated component

The list of MedDRA preferred terms used to identify Immune-Mediated adverse events is revisited quarterly and updated accordingly. The preferred terms used for the selection at the time of the database lock by categories will be provided. IMAEs will be summarized for Parts 2 and 3 only for each immune mediated category/PT. A by-participant listing of IMAEs will be provided. A listing of AEs considered as Immune-Mediated Events per Investigator as recorded on the CRF but not Qualified for Immune-Mediated AE Definition will also be provided.

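### SAP 5.1.3 counts bladder hemorrhage and cytokine release by one preferred term each, so related events fall outside these primary-endpoint rows and urine blood has no named summary

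*SAP*

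**What the plan says.** Protocol Table 4-1 gives as its third primary endpoint "Vital sign abnormalities or other safety biomarkers". Protocol 10.3.2 states the method only as "Frequency statistics of renal function and bladder hemorrhage" and supplies no term list.

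SAP 5.1.3 turns this into codes:

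- Bladder hemorrhage: "MedDRA Preferred Term: Urinary Bladder Hemorrhage", with no laboratory component.
- Cytokine release monitoring: "MedDRA Preferred Term: Cytokine Release Syndrome", with no cytokine values.
- Renal function: "MedDRA Preferred Terms: Nephritis and Renal Failure", together with blood creatinine values.

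SAP 8.6.12 provides frequency statistics for the three event measures and summary statistics for creatinine. It lists the cytokine assay results without summarizing them. Under SAP 8.6, safety output is presented by part and dose level.

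On the data side, Protocol Table 9.4.5-1 requires "Urinalysis including protein, glucose, blood, leukocyte esterase, specific gravity, PH", with microscopy of the sediment when blood, protein or leukocyte esterase is positive on the dipstick.

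**The concern.** The protocol does not ask for single-code measures; that restriction enters with the SAP. A row labelled bladder hemorrhage or cytokine release, sitting under a primary endpoint of a first-in-human virus study, will be read as the count of that kind of event at each dose level. If related events carry another code, the row can be low or empty while the signal is spread over several lines of other tables. For the bladder, the study also collects an objective measure, blood in urine, that the row does not use.

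**Working it through.** No arithmetic applies. The measures are descriptive, and the documents state no rate, sample size or error level for them. The check is whether anything else in the SAP supplies what the rows leave out.

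**1. How the SAP treats similar events elsewhere.** SAP 8.6.9 builds immune-mediated events from "groups of PTs describing specific events", including a nephritis/renal dysfunction category. SAP 8.6.7 builds select events from term lists by category. In 5.1.3 the same document falls back to one or two exact terms.

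**2. Whether grouped output covers the gap.**

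- SAP 8.6.9 summarizes immune-mediated events for Parts 2 and 3 only, and only events meeting further conditions, such as (outside the endocrine events) treatment with immune-modulating medication. Part 1, the monotherapy dose escalation, gets no grouped renal row from it.
- SAP 8.6.7 says custom queries for BMS-986277 may be defined, and for Part 1 the list applies if it exists. No bladder, hematuria or infusion-reaction category is named. SAP 5.1.1 likewise allows extra categories relevant to BMS-986277 without naming any.

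A grouped count is therefore possible but not committed to.

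**3. Whether the general tables cover it.** SAP 8.6.6 tabulates all adverse events by system organ class and preferred term. That shows each related term, but one line at a time. A participant can appear on two lines, so the lines cannot be added to give participants with any related event.

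**4. Urine blood.** Urinalysis is marked at every visit column of Protocol Tables 2-2, 2-3 and 2-4 (Part 1, Part 2, Part 3 Cohorts 1-2). In Table 2-5 (Cohort 3) it is marked at Day 1 of each cycle and at end of treatment. Protocol 9.2.6 has a laboratory abnormality recorded as an adverse event only if it is clinically significant, meets the serious definition, leads to interruption or discontinuation, or needs corrective therapy. Lesser findings of urine blood need never reach an adverse event term. SAP 8.6.10 lists laboratory results outside the normal range. Its summaries are built on CTC grade, and it does not say how a urine result would enter them.

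**5. Cytokine release and infusion reactions.** Protocol 7.4.5 discusses cytokine release under the management of infusion reactions, and the Document History entry for Revised Protocol 06 says one treatment algorithm "applies to both infusion reactions and cytokine release syndrome". These are two labels that the protocol places close together, and the SAP row counts one of them. The assay data are a limited backstop, because Protocol 9.4.1 has samples analyzed only as clinically indicated.

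**6. Creatinine.** It has summary statistics in 8.6.12. It is also one of the chemistry tests in Protocol Table 9.4.5-1, so the CTC-grade shift table in 8.6.10 applies to it. Nothing is missing here except a cross-reference.

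**The case against.** The incidence of all adverse events is itself a primary endpoint. Hematuria or an infusion reaction reported as an adverse event is tabulated under its own term, by worst grade, part and dose level, and again if serious or leading to discontinuation. Infusion reactions that meet the dose-limiting criteria are also counted in SAP 8.6.1. On this view the rows in 8.6.12 are a supplement, and a reader would have to ignore the main tables to be misled. A mechanism for grouped terms already exists in 8.6.7. A shared treatment algorithm does not make two reactions one analysis category, and pooling nivolumab infusion reactions with cytokine release could blur a signal specific to the virus. Appendix 10 and most of the protocol introduction are redacted, so a reason for the narrow choice may exist unseen.

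Much of this stands. A reader might infer that these events go uncounted or that urinalysis is unused; the documents support neither. The events are counted elsewhere, and out-of-range laboratory results are listed, with urinalysis neither named nor excluded. The warning about pooling also stands and shapes the fix. What does not follow is that the existing outputs close the gap: the grouped queries are optional, the immune-mediated groups are not summarized for Part 1, and term-by-term tables give no participant count across related terms.

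**Conclusion.** The point holds in a limited form. As written, the bladder and cytokine rows leave out any event coded to a related term, the renal row does so beyond its two terms, and urine blood does not feed the bladder measure. This makes named components of a primary endpoint less informative than the collected data allow. It does not remove events from the study report.

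The size of any undercount cannot be estimated. A reader might attach a figure by assuming an incidence and a share of events captured by the named term. The documents supply neither for BMS-986277, so such a figure would only restate its assumptions. The conclusion also rests on the assumption that related events do code to other preferred terms. That is a property of MedDRA, which the documents do not reproduce. This is an inexpensive improvement to the reporting, not a flaw that threatens the safety conclusions.

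**What to change.** Before database lock, amend SAP 5.1.3 and 8.6.12 as follows.

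- **Renal:** use the nephritis/renal dysfunction term list of 8.6.9, applied to Part 1 as well. For creatinine, cross-refer to the shift table in 8.6.10.
- **Bladder:** use a listed group of bladder bleeding and hematuria terms. Add a shift table of urine blood, baseline to worst on-treatment result, by dose level.
- **Cytokine release:** keep cytokine release syndrome as its own row, show infusion reactions as a separate row beside it, and add a combined row, so that the cytokine signal is not diluted.
- **Counting:** report participants with at least one event in each group, by part and dose level, with the current single terms kept as sub-rows.

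The cost is SAP text, fixed term lists and a few tables from data already collected. SAP version 1.0 incorporates changes only up to Revised Protocol 03 and still describes two expansion cohorts and up to three cycles of BMS-986277 in Parts 2 and 3. The current protocol has three cohorts and up to two cycles, so a revision is needed in any case. The downside is that broader groups will include some unrelated events; the sub-rows let a reader see how many.

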# 5.2 Secondary Endpoints

The secondary objectives relate to preliminary anti-tumor activity, pharmacokinetics, and immunogenicity of BMS-986277 alone and/or in combination with nivolumab in advanced epithelial tumors.

# 5.2.1 Preliminary Anti-Tumor Activity

Changes in tumor measurements and tumor response will be measured based on RECIST v1.1 (all indications except PRC) or PCWG3 (PRC participants only), hereafter referred to collectively as "RECIST 1.1/PCWG3". Tumor assessments will be performed at baseline, and then approximately every 8 weeks (all indications except PRC) or every 8 weeks for 24 weeks and then every 12 weeks afterward (for PRC participants). Tumor assessment should continue until disease progression (ideally confirmed with second assessments obtained at least 4 weeks apart) or discontinuation of study treatment, withdrawal from study, or start of subsequent anticancer treatment, whichever occurs later. For PRC participants, any clinical progression due to symptomatic skeletal events detected during bone scans may be counted as a progression event.

The following set of efficacy study-level endpoints will be used:

- **Objective Response Rate (ORR)**: The ORR is defined as the total number of participants whose best overall response (BOR) is either a complete response (CR) or partial response (PR) divided by the total number of participants in the population of interest (eg, all treated participants or response-evaluable participants).
  - The BOR for a participant will be assessed by investigator and/or by BICR, where available.
    - ♦ For interim analyses or internal monitoring of efficacy before the final BOR can be determined, the BOR (including a category for unconfirmed responses still in follow-up) may be derived using an internal algorithm.
  - The BOR for a participant is defined as the best response designation recorded between the date of first study drug administration and the date of first objectively documented progression per RECIST 1.1/PCWG3 or date of subsequent anticancer therapy, whichever occurs first.
    - ♦ For those participants who have surgical resection, only pre-surgical tumor assessments will be considered in the determination of BOR.
    - For participants without documented progression or subsequent anticancer therapy, all available response designations will contribute to the BOR assessment.
    - ♦ For participants who continue treatment beyond progression or begin subsequent anticancer therapy, the BOR should be determined based on response designations recorded up to the time of the initial RECIST 1.1/PCWG3-defined progression or subsequent anticancer therapy, whichever occurs first.
    - For a BOR of CR or PR, the response assessment must have been confirmed by a consecutive assessment meeting the criteria for response and performed no less than 4 weeks (28 days) after the criteria for response are first met.

- ♦ A BOR of stable disease (SD) can only be made after the participant is on-study for a minimum of 49 days from the date of treatment initiation (i.e., first dose).
- **Disease Control Rate (DCR)**: The DCR is defined as the total number of participants whose BOR is CR, PR, or SD, divided by the total number of participants in the population of interest (eg, all treated or response-evaluable).
- **Median Duration of Response (mDOR)**: The significance of ORR is assessed by its magnitude and duration of response.
  - The DOR for a participant will be calculated for participants with BOR of CR or PR only, and is defined as time between the date of first objectively documented response (which is subsequently confirmed) and the date of first subsequent objectively documented disease progression per RECIST v1.1/PCWG3 or death due to any cause, whichever occurs first.
    - ◆ For interim analyses or internal monitoring, DOR may also be calculated for unconfirmed responses.
  - Participants who remain alive and have not progressed will be censored on the date of their last evaluable tumor assessment (prior to subsequent anticancer therapy).
  - Participants who receive subsequent anticancer therapy without a prior documented disease progression will be censored on the date of their last evaluable tumor assessment prior to initiation of the subsequent anticancer therapy.
- Median Progression-Free Survival (mPFS): The median of all participants' PFS is considered the study-level endpoint and is estimated using the Kaplan-Meier method.
  - The PFS for a participant is defined as the time from the first dosing date to the date of first objectively documented disease progression per RECIST v1.1/PCWG3 or death due to any cause, whichever occurs first.
  - Participants who died without a reported prior progression will be considered to have progressed on the date of their death.
  - Participants who remain alive and have not progressed will be censored on the date of their last evaluable tumor assessment (prior to subsequent anticancer therapy).
  - Participants who receive subsequent anticancer therapy without a prior documented disease progression will be censored on the date of their last evaluable tumor assessment prior to initiation of the subsequent anticancer therapy.
  - Participants who did not have any post-baseline tumor assessment and did not die will be censored on the date of first dose of study medication.
  - Clinical deterioration in the absence of radiographic evidence is not considered progression for the purpose of determining PFS per RECIST v1.1/PCWG3 when using objectively documented progression.
- **Progression Free Survival Rate (PFSR) at Week t**: The proportion of participants in the population of interest remaining progression free and surviving to time t, where t is a specific length of time, eg, 8, 16, or 24 weeks, which will depend on the indication and also be determined by the available data for each interim or final analysis. The specific length of time will be documented in the data presentation plan (DPP). The proportion will be calculated by the product-limit method (Kaplan-Meier estimate) which takes into account censored data.

